5.1.4 Per-protocol (PP) population

The per-protocol population was defined as all patients who received the 2 or 4 planned DEBIRI sessions and met the inclusion/exclusion criteria of the study.

6 General information about statistical methods

Statistical analyses will be performed by the CRGA.

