Study design and treatment plan	
Microbeads (100-300μm), loaded with irinotecan (DEBIRI). The maximum dose per procedure is 100 mg of irinotecan, combined with intravenous FOLFOX.
 
For patients with unilobar or bilobar liver involvement, DEBIRI will be injected at D17 and D45 (after the 2nd and 4th cycle of systemic chemotherapy with FOLFOX).
 
Patients with bilobar involvement but for whom the investigator decides that the treatment will be unilobar and sequential, there will be 4 sessions. Thus, the right and left livers will be treated alternately. The DEBIRI administrations will then be performed at D17, D31, D45, D59, or in case of a shift in chemotherapy treatment, after the 2^{ème}, 3^{ème}, 4^{ème} and 5^{ème} cycle of FOLFOX.
 
FOLFOX will be administered every 2 weeks until progression or unacceptable toxicity.

Statistical methods	
A 1-step Fleming design will be used, with a one-sided α risk of 5% and a power (1-β) of 90%.
 
The assumptions are:
 
 • H0: A proportion of patients living without progression of 55% during the first 9 months is uninteresting; • H1: A proportion of patients living without progression of more than 55% during the first 9 months would show the interest of the treatment; a proportion of 75% is hoped for.

	
Total number: 48 evaluable patients
 
Taking into account a 20% rate of lost to follow-up or non-evaluable patients, 58 patients should be included.
 
At the end of recruitment:
 
During analysis:
 
 - if 32 or fewer patients are alive without progression, then the treatment is considered ineffective - if 33 or more patients are alive without progression, then the treatment is considered effective 
The decision rule will be adjusted based on the actual number of evaluable patients.

Number of subjects needed	58
Associated translational studies	
 - On lipid parameters: The objective of this study will be to evaluate the impact of the different parameters of the lipid profile and the metabolism of lipoproteins on the response to treatment. - On Pathology: At the end of the study, if a sufficient number of patients have undergone secondary resections of liver metastases, a collection of surgical parts will be organized. An anatomopathological study of the tumor parenchyma and the healthy parenchyma resected after DEBIRI treatment will be performed.

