- If the following grade 3 or 4 toxicities occur as a result of chemoembolization, no additional session will be performed (but FOLFOX will be continued).

- Arteritis
- Grade 3 or 4 hepatic impairment
- Local ischemic and septic manifestations (cholecystitis, hepatic infarction, hepatic abscess, digestive hemorrhage) of grade 3 or 4
- Grade 3 or 4 renal insufficiency
- **The interval between chemoembolization sessions may be extended to allow for recovery of liver function.**
- No dose adjustment of irinotecan is planned for chemoembolization sessions.
- In case of hematological toxicity, FOLFOX dose adjustment rules **will be applied and chemoembolization will be continued.**

In case of doubt, do not hesitate to ask for advice from the study's referring radiologist, [name], through the FFCD.

VII. PATIENT MONITORING DURING TREATMENT AND AFTER WITHDRAWAL OF TREATMENT

Monitoring during treatment:

- **Before each cycle of FOLFOX:**
 - Complete clinical examination including: weight, vital signs, WHO, pain assessment (VAS)
 - Biological check-up: CBC/platelets
 - Adverse event evaluations according to NCI CTC version 4.0
- **Before each chemoembolization session**
 - Complete clinical examination including: weight, vital signs, WHO, pain assessment (VAS)
 - Biological workup consisting of measurements of hematological, nephrological and hepatic parameters: CBC/platelets, blood ionogram, creatinine, albumin, transaminases (AST, ALT), alkaline phosphatases (ALP), total and conjugated bilirubin, PT
 - Adverse event evaluations according to NCI CTC version 4.0

CEA and CA 19-9 assays, as well as thoracoabdomino-pelvic CT and liver MRI will be performed at an initial evaluation between D63 and D70 and then every 2 months after the start of treatment.

For patients participating in the associated 'lipid' translational study, please remember to perform the fasting sample and then technician the sample.

After the chemoembolization treatment period:

All patients will receive chemotherapy with FOLFOX every 2 weeks according to the usual regimen until progression or unacceptable toxicity.

VIII. STOP PROCESSING THE STUDY

The processing of the study will be stopped in case of:

- Investigator's decision
- Major toxicity requiring discontinuation of treatment (despite protocol adaptations)
- Serious or unexpected event requiring discontinuation of protocol treatment
- Progression of the disease
- Patient refusal or withdrawal of consent

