The primary endpoint will be the proportion of patients alive without progression (death will be considered as progression) at 9 months after the start of treatment according to RECIST V1.1 criteria, as assessed by the investigator.

Progression-free survival time will be defined as the time interval between the date of inclusion and the date of progression or death (regardless of cause). For patients alive without progression, the time interval between the date of inclusion and the date of last morphological evaluation will be taken.

XII.2.2 Secondary Criteria

The secondary endpoints will be:

- Tolerance to the treatment
- Response rate according to RECIST v1.1 criteria at 9 months (according to the investigator)
- Response rate according to EASL criteria (assessed by centralized review) at 9 months
- Hepatic progression-free survival according to RECIST v1.1 criteria at 9 months
- Overall survival
- Progression-free survival
- The rate of secondary resections
- Changes in tumor marker levels

Liver progression-free survival will be defined as the time interval between the date of inclusion and the date of liver progression as assessed by the investigator's RECIST V1.1 criteria or death (regardless of cause) or the date of the last morphological assessment for patients alive without progression.

Overall survival will be defined as the time interval between the date of inclusion and the date of death regardless of the cause of death or the date of last news for living patients.

Tolerance to treatment will be assessed by:

- duration of treatment, doses received, dose reductions and deferrals
- Toxicities collected at each monthly visit, and described according to NCI-CTC version 4.0 criteria; Grade 3, Grade 4 and Grade 5 toxicities will be reviewed
- the number and description of SAEs

Changes in tumor marker levels (CEA and CA 19-9) will be assessed throughout the study.

XII.3 Calculation of the number of subjects needed

A 1-step Fleming design will be used, with a one-sided α risk of 5% and a power (1- β) of 90%.

The assumptions are:

- H0: A proportion of patients living without progression of 55% during the first 9 months is uninteresting;
- H1: A proportion of patients living without progression of more than 55% during the first 9 months would show the interest of the treatment; a proportion of 75% is hoped for.

Total number: **48 evaluable patients**

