4.3 Justification of the number of subjects needed

A 1-step Fleming design was used, with a one-sided α risk of 5% and a power ($1-\beta$) of 90%.

The clinical assumptions made were:

H_0 : A 55% progression-free live proportion during the first 9 months is unattractive;

H_1 : A proportion of patients alive without progression of more than 55% during the first 9 months would show the interest of the treatment; a proportion of 75% is hoped for.

48 evaluable patients were required. Taking into account a 20% rate of patients lost to follow-up or not evaluable, 58 patients were to be included.

The decision rules are as follows: of the 48 evaluable patients

- If 32 or fewer patients are alive without progression, then the treatment is considered ineffective
- If 33 or more patients are alive without progression, then the treatment is considered effective

The decision rule will be adjusted based on the actual number of evaluable patients.

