6.5 Statistics

The confidence intervals provided will be two-sided 95% confidence intervals except for the primary endpoint where the calculated confidence interval will be a one-sided 95% confidence interval.

Quantitative data will be described using the following descriptive statistics: number, mean, standard deviation, median, first and third quartile, and minimum and maximum. These statistics will be considered the usual statistics for the analysis of quantitative variables. Quantitative variables can be categorized using their median or a cut-off known from the medical literature.

Categorical variables will be summarized, using the following descriptive statistics: the number, frequencies and percentages for each level of the variable. These statistics will be considered as the usual statistics for the analysis of categorical variables.

When necessary, the 95% confidence intervals for the proportions can be calculated from the exact binomial distribution.

Survival data will be estimated and plotted using the Kaplan Meier method (Kaplan and Meier, 1958). They will be described by the median and rates calculated at different time points with their two-sided 95% confidence intervals. The confidence intervals for the rates will be constructed from the Greenwood variance calculated using the log-log transformation.

The median follow-up time will be estimated by the reverse Kaplan-Meier method (Shemper, 1996).

As an exploratory measure, for the uni and multivariate analyses, the hazard ratios will be estimated using a Cox model (Cox, 1984). The hypothesis of proportionality of the rates will be tested using the graphical representation and the test based on Schöenfeld's residuals (Grambsch, 1994); the linearity of the effect of the continuous variables on the risk will be evaluated from the graphical representation of the martingale residuals. Confidence intervals for the coefficient estimates of the Cox models will be calculated using the Wald method.

7 Statistical analysis

	Population ITT	Population ITTm	Tolerance population	Population Per protocol
Description of Baseline				
Eligibility criteria for inclusion	X	X		X
Demographic characteristics	X	X		X
Clinical characteristics at inclusion	X	X		X
Biological characteristics at inclusion	X	X		X
Characteristics related to the disease	X	X		X
Median follow-up time	X	X		X
Main criterion				
Progression-free survival rate at 9 months	X	X		X
Secondary criteria				

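### The per-protocol set is defined by completing every planned DEBIRI session, so it excludes patients stopped as the protocol directs and gives completers guaranteed survival to D45 or D59

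*SAP*

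**What the plan says.** SAP 5.1.4 defines the PP set as "all patients who received the 2 or 4 planned DEBIRI sessions" who also satisfied the eligibility criteria. It makes no exception for sessions stopped for a reason the protocol provides for.

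The protocol provides for several such reasons:
- Protocol VI.2: after listed grade 3 or 4 toxicities due to chemoembolization, "no additional session will be performed (but FOLFOX will be continued".
- Protocol VI.2 also stops a procedure on technical grounds, such as failure to catheterize the hepatic artery.
- Protocol VIII ends study treatment at progression or major toxicity.
- Protocol V.2.6 requires adequate liver function and blood counts before each session.

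The last planned session falls at D45 (two sessions) or D59 (four sessions). The first scheduled imaging is at D63 to D70 (Protocol VII).

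The SAP section 7 table marks the PP column for "Progression-free survival rate at 9 months", and also for PFS and OS. The 9-month endpoint runs from day 1 of cycle 1 (SAP 7.3.1). PFS and OS run from inclusion (SAP 7.4.6.1 and 7.4.7.1). The primary analysis and the decision rule use the mITT set, which the SAP calls ITTm (SAP 7.3 and 7.3.2). Protocol XII.4 defines no PP set.

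**The concern.** A per-protocol set is normally meant to remove patients who departed from the protocol. This one removes patients who followed it: someone whose sessions were halted under VI.2 and who stayed on FOLFOX was treated as directed, yet does not count as per protocol.

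Entry also requires surviving to the last session and, in practice, having no recognised progression before it. The time axis nevertheless starts at inclusion or cycle 1, so up to D45 or D59 is time in which a PP patient could not have died. For OS this is immortal time whatever the scan schedule.

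At stake is how a supportive efficacy figure is read. It will be tabulated beside ITT and mITT, and a higher PP rate could be taken as a benefit of completing DEBIRI. SAP 5.1.2 promises a listing of patients excluded from mITT with reasons. No such listing is promised for PP.

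**Working it through.** **The plan's own figure.** Inputs are "A proportion of patients living without progression of 55% during the first 9 months is uninteresting" (Protocol XII.3), "a proportion of 75% is hoped for" (SAP 4.3), one-sided alpha 5% and power 90%. The one-sample normal approximation gives n = [(1.645·√(0.55·0.45) + 1.282·√(0.75·0.25)) / 0.20]² = 47.14, rounded up to 48, in agreement with "48 evaluable patients were required". The cutoff of 33/48 has an exact one-sided alpha of 3.69% under a 55% rate. This rule is applied to mITT, not to PP.

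**Worst case against an unselected population.** Assume a constant hazard and a 9-month rate of 55%, and that every patient with an event before the last session is dropped.
- 9 months = 9 × 30.4375 = 273.9 days, using the SAP 6.2 conversion.
- λ = −ln(0.55)/273.9 = 0.00218 per day.
- S(45) = exp(−45λ) = 0.906, so 9.4% of patients, or 21% of all 9-month failures, fall before D45. PP rate = 0.55/0.906 = 60.7%.
- S(59) = exp(−59λ) = 0.879, so 12.1% of patients, or 27% of failures, fall before D59. PP rate = 0.55/0.879 = 62.6%.

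**Worst case in counts.** If 26 of 48 succeed (54.2%) and 4 to 8 non-completers all failed, PP would show 26/44 = 59.1% to 26/40 = 65.0%. Neither the number dropped nor their failure is in the documents.

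**Less extreme cases.** With overall rate p, share dropped f and rate q among those dropped, the PP rate is (p − f·q)/(1 − f). The documents give neither f nor q, so both are assumed. With p = 55%:

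| q among those dropped | f = 5% | f = 10% | f = 20% |
|---|---|---|---|
| 0% | 57.9% | 61.1% | 68.8% |
| 30% | 56.3% | 57.8% | 61.3% |
| 55% | 55.0% | 55.0% | 55.0% |
| 65% | 54.5% | 53.9% | 52.5% |

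Dropping early deaths and progressions can only raise the rate. Dropping patients stopped for toxicity can move it either way, since they continue FOLFOX and their outcome is unknown.

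**Why the gap against mITT is probably smaller.** Two features limit it:
- When sessions run on time, the first scheduled scan comes after the last session, so few radiological progressions can be found early enough to prevent completion. What remains is death, progression found on unscheduled imaging or clinically, and delayed sessions. Protocol VI.2 lets the interval between sessions be extended and states no limit, so a late last session can fall after the first scan.
- SAP 5.1.2 already requires a chemoembolization and at least one assessment for mITT. If assessment means tumour evaluation, a patient who dies before any imaging is outside mITT too, and so adds nothing to the difference between PP and mITT.

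**The case against.** The strongest reply is that nothing rests on this set. The primary endpoint and its rule are assessed on mITT, SAP 7.4.6 and 7.4.7 name ITT for PFS and OS, and PP is only an extra column in the table with no test attached. Defining a set by treatment received is a familiar convention, and the selection is stated openly. SAP 7.5.1 also has the causes described for patients who did not have all their sessions. All of this stands, and it limits the point to a supportive analysis. It does not justify the label: the set is called per protocol yet excludes adherent patients. Describing causes does not show how those patients fared at 9 months.

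A second reply is that no inflation has been shown. This also stands. A reader might infer that the PP rate is certainly inflated, or that the worst-case figures estimate by how much. The documents do not support that, because they give no share of non-completers and no outcomes for them. If non-completers did as well as the rest, the rate would not move. If they did better, it would fall.

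A third reply is that keeping every stopped patient could put into PP some who never had a chemoembolization and are therefore outside mITT. That is right, and the redefinition has to be nested within mITT.

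**Conclusion.** The point holds as a minor one about a supportive set. The definition selects on events after inclusion, excludes patients treated as the protocol directs, and builds guaranteed survival into estimates timed from inclusion or cycle 1. The expected bias is upward. Its size, and even its sign, depend on outcomes that the documents do not give.

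The figures of 60.7% and 62.6% are a worst case. They assume a 55% rate, a constant hazard and the removal of every patient with an event before the last session, and they compare with an unselected population rather than with mITT. A reader might also infer that the trial's conclusion is at risk. It is not, because the 33/48 decision uses mITT and no rule is applied to PP.

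**What to change.** Before database freeze, choose one of two changes to SAP 5.1.4:

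1. **Redefine PP.** Within mITT, take patients without major eligibility or treatment deviations, with the deviations listed in the SAP. Keep those whose sessions stopped under protocol rules or because of progression or death.
2. **Rename the set.** Call it DEBIRI completers and label its 9-month rate as descriptive. Analyse its PFS and OS from a landmark at the last planned session, and classify completion as it stands at that landmark, because delayed sessions would otherwise bring guaranteed time back.

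Under either option, list the exclusions with the reason and 9-month status. Also state whether a session cut short at near-stasis counts as received; Protocol V.2.7 foresees such sessions and the SAP is silent.

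The cost is SAP wording and a reclassification of patients. The downsides are a possibly less favourable supportive figure and, under the first option, a PP set closer to mITT and so less distinct as a sensitivity analysis.

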6.1 Software

Statistical analyses will be performed with SAS software version 9.4. Some graphs can be made with R software version 2.11 or later.

6.2 Agreements concerning dates and durations

Time since inclusion will be defined as the time since the day of inclusion, with the day of inclusion considered day 1. Therefore, the durations will be calculated according to the following rule, for example for the duration between death and inclusion: day of death - day of inclusion **+ 1**.

The day before the day of inclusion (resp. the day before the day of treatment) will be considered as day -1 (day 0 does not exist).

The last date of news will be the date of the last examination performed or the last treatment or the last medical consultation/visit.

The following conversion rules will be used to convert the number of days into months or years: 1 month = 30.4375 days; 1 year = 365.25 days.

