In all cases of treatment discontinuation, the patient remains in the analysis for intention-to-treat and overall survival, and for 30 days after the last study treatment for toxicity.

There is no exclusion period for a subsequent therapeutic trial.

IX. CENTRALIZED READING OF CT SCANS AND MRI

Responses will be evaluated according to RECIST version 1.1 criteria (Appendix 3) and will be reviewed by a panel of independent radiologists according to RECIST version 1.1 criteria and EASL criteria (Appendix 4).

Don't forget to keep the CDs and the report of the CT and MRI evaluation in the patient's file; the FFCD CRA will make a copy of these imaging assessments to centralize them at the CRGA on the 'FFCD Images' platform using a secure transmission via the company ETIAM.

X. MANAGEMENT OF SERIOUS ADVERSE EVENTS (SIA)

Safety will be assessed by evaluating the general, clinical and biological status of patients at the time of scheduled visits and by collecting events occurring between visits. Toxicities will be assessed using the NCI-CTC Toxicity Scale version 4.0 (Appendix 5).

X.1 Definitions

Adverse Event (AE)

An adverse event is a harmful occurrence in a person who is a subject of biomedical research, whether or not the occurrence is related to the research or the product being investigated. All adverse events will be recorded in the observation book on the pages provided.

Serious Adverse Event (SAE)

A serious adverse event is any event that meets at least one of the following criteria:

- Resulting in death,
- Life-threatening,
- Leading to hospitalization or prolonged hospitalization,
- Causing permanent disability or severe temporary incapacity,
- Causing a birth defect, fetal malformation or abortion,
- Medically significant (examples: overdoses, second cancers, pregnancies and new developments may be considered medically significant)

Pregnancy is an exclusion criterion in this trial.

However, if a pregnancy is discovered after inclusion, the patient must be excluded from the trial. The sponsor should be informed immediately via the Serious Adverse Event Reporting Form (no severity criteria should be checked). The patient should be followed until the outcome of the pregnancy and this outcome, whatever it may be, should be reported to the sponsor.

Hospitalizations included in the protocol will not be considered an SAE.

Undesirable Effect

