7.4.7.1 Definition of overall survival

It is defined as the time interval between the date of inclusion and the date of death (regardless of cause).

Patients lost to follow-up or alive at the time of analysis will be censored at the date of last report.

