7.4.7.2 Evaluation of overall survival

The time scale considered will be the month.

Overall survival will be plotted using the Kaplan Meier estimator and survival rates at different time points (6, 9, 12 and 18 months) will be calculated along with their 95% confidence intervals.

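### Overall survival is censored at the last clinical contact, with no common cut-off date or vital-status check, so the censoring may be informative in a direction the documents do not settle

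*SAP*

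**What the plan says.** SAP 6.2 defines the date on which follow-up of a living patient ends: "The last date of news will be the date of the last examination performed or the last treatment or the last medical consultation/visit". It lists clinical contacts only. A telephone call, a letter from the treating physician or a vital-status record is not among them.

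SAP 7.4.7.1 defines OS from inclusion to death from any cause and adds: "Patients lost to follow-up or alive at the time of analysis will be censored at the date of last report". That section does not define the date of last report, so I read it as the last date of news in SAP 6.2. Protocol XII.2.2 ends OS at the date of death "or the date of last news for living patients", with no further definition. SAP 7.4.7.2 plans Kaplan-Meier output: "survival rates at different time points (6, 9, 12 and 18 months) will be calculated along with their 95% confidence intervals". Medians are also planned (protocol XII.4, SAP 6.5).

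On follow-up after treatment, protocol VIII says: "In all cases of treatment discontinuation, the patient remains in the analysis for intention-to-treat and overall survival". It gives no visit frequency. Protocol VII is headed "PATIENT MONITORING DURING TREATMENT AND AFTER WITHDRAWAL OF TREATMENT", but the text beneath sets examinations before FOLFOX cycles and chemoembolization sessions. It also sets imaging and markers that "will be performed at an initial evaluation between D63 and D70 and then every 2 months after the start of treatment", listed under monitoring during treatment with no stated end. SAP 4.4 plans a single final analysis and gives no cut-off date. Neither document asks for a vital-status update before it.

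**The concern.** The two outcomes are not dated by the same rule. A death in the database counts on the day it happened. Survival counts only up to the last recorded clinical contact. Suppose two patients leave treatment at progression and both are traced a year later by telephone. If one has died, that patient contributes an event at the date of death. If the other is alive, that patient is censored at the last clinical contact, and the extra year is lost. Whether a patient is censored early then depends on whether the patient has died. Kaplan-Meier estimation assumes that it does not.

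The opposite error is also possible. If contact is lost and the later death never reaches the database, the patient is censored around progression, when prognosis is worse than for those who remain at risk. That pushes the curve up.

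The OS rates, the OS median and the exploratory Cox models for OS (SAP 7.6) are all exposed. Follow-up time in SAP 7.2 runs to the same date for living patients and is estimated by reverse Kaplan-Meier, so it may be understated.

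**Working it through.** **1. The plan's own figure.** The documents state no OS assumption or target. The only design figure is 48 evaluable patients for the primary endpoint. The one-stage normal formula reproduces it: [(1.645·√(0.55·0.45) + 1.282·√(0.75·0.25)) / 0.20]² = 47.14, rounded up to 48. The primary endpoint is classified from scans and deaths around 9 months (SAP 7.3.1) and does not use the last-news date.

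**2. What a common cut-off would give.** Protocol XII.1 ends inclusion in April 2015 and the study in July 2017, which is 27 months. The synopsis dates (April 2016, July 2018) also give 27 months. If every patient's status is known at study end, nobody alive is censored before 27 months. OS at 6, 9, 12 and 18 months is then simply the proportion alive. If instead each living patient has a contact within 6 months of the cut-off, the earliest censoring is at 27 − 6 = 21 months. That is after 18 months, so no planned rate changes.

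**3. Simulation of the SAP rule.** OS is time to progression plus survival after progression, both exponential. These inputs are assumptions, not in the documents:
- set A: medians of 9 and 14 months;
- set B: medians of 11 and 18 months.

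They imply 9-month progression-free rates of 0.5^(9/9) = 50% and 0.5^(9/11) = 57%, close to the plan's 55% null value. Accrual is 24 months (XII.1) or 36 months (synopsis), and minimum follow-up is 27 months. With complete status at cut-off, 18-month OS is about 70% (A) or 78% (B), and the median about 27.5 or 34.6 months. Each scenario uses 400,000 patients, so the differences show bias and not sampling error.

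Cells give the change in 18-month OS (points) / change in median (months), SAP rule minus complete status:

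| Scenario | A, 24 | A, 36 | B, 24 | B, 36 |
|---|---|---|---|---|
| Contact every 2 months to cut-off, all deaths captured | 0 / 0.0 | 0 / 0.0 | 0 / −0.4 | 0 / −0.2 |
| Contact every 6 months to cut-off, all deaths captured | 0 / −0.4 | 0 / −0.2 | 0 / −1.4 | 0 / −0.9 |
| Contact stops at progression, 100% of deaths captured | −4.0 / −3.9 | −3.1 / −3.2 | −3.9 / −7.0 | −3.1 / −6.0 |
| Same, 90% captured | −2.3 / −3.1 | −1.5 / −2.4 | −2.3 / −6.1 | −1.7 / −5.1 |
| Same, 75% captured | +0.5 / −1.8 | +1.2 / −1.1 | +0.2 / −4.6 | +0.8 / −3.5 |
| Same, 50% captured | +6.8 / +1.4 | +7.4 / +2.3 | +5.5 / −0.6 | +5.8 / +0.8 |

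For example, A with 24 months' accrual and all deaths captured gives 65.8 − 69.8 = −4.0 points and 23.7 − 27.6 = −3.9 months. When contact stops at progression, the sign at 18 months changes somewhere between 10% and 25% of deaths missed.

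**4. A second model, for partial loss of contact.** Assume exponential OS with median 24 months, 9-month PFS 55%, accrual over 24 months, all deaths known, and contact lost 1 month after progression. True 18-month OS is 59.5%. If 30% of living progressed patients lose contact, the estimate is 58.4% with a median of 22.9 months. If all do, it is 55.2% with a median of 20.4 months. With 9-month PFS of 75% and all losing contact, it is 59.2% with a median of 23.6 months.

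This model holds the death hazard constant before and after progression. The death hazard is ln 2/24 = 0.0289 per month and the PFS hazard −ln(0.55)/9 = 0.0664, so 43% of PFS events would be deaths without progression. At 75% PFS the share is 0.0289/0.0320 = 90%. It shows how far the size depends on the model and is not an effect estimate.

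**5. Scale.** With 58 patients and true 18-month OS of 69.8%, the standard error is √(0.698·0.302/58) = 0.060, a 95% half-width of about 12 points. A bias of 3 to 4 points is about a third of that.

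**The case against.** Three stronger readings are tempting, and the documents support none of them.

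- **That OS is biased downward.** This needs nearly all late deaths to be known, and the documents do not say how late deaths reach the sponsor. The one reporting route described, SAE notification in protocol X.2, ends 30 days after the last treatment unless the event is considered related. With 75% or fewer of deaths captured, the table shows 18-month OS too high.
- **That a death counts however it is learned.** SAP 7.4.7.1 speaks of cause of death, not source of information. It sets no restriction on source, and that is as far as the text goes.
- **That no visits take place after treatment.** The heading of protocol VII announces such monitoring, the two-monthly imaging has no stated end, and figures and appendices are missing from the available text. One can say only that the text at hand gives no frequency.

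The SAP rule is also wider than trial visits. A treatment or consultation can belong to a later line, and SAP 7.5.2.4 expects data on later lines and later chemoembolization. Patients who could not be followed regularly are excluded at entry. Complete loss of contact at progression is therefore an extreme case. Finally, OS is secondary and descriptive in a single-arm trial with no OS hypothesis.

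All of this stands. It limits the likely size and rules out a firm direction. It does not remove the asymmetry in dating, and nothing in the plan guarantees the contact that would make it harmless. The missing words for 'the latest of' in SAP 6.2 are trivial, since a last date already means the latest.

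**Conclusion.** The point holds as a conditional one. SAP 6.2 ends a living patient's OS time at the last clinical contact, while a recorded death counts at its own date. The available text sets no post-treatment visit frequency, no common cut-off and no vital-status update. OS censoring may therefore be informative.

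Under the assumed inputs of step 3, 18-month OS is up to about 3 to 4 points low and the median about 3 to 7 months low if contact stops at progression and nearly all deaths are captured. The 18-month bias is nil if contact continues to near cut-off. It turns upward if a material share of later deaths is missed. Which case applies cannot be read from the documents, so no single figure should be quoted as the effect. The decision rule of 33 or more of 48 is untouched. I would label this a cheap improvement.

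**What to change.** - In SAP 6.2, define the date of last news **for OS and follow-up time** as the latest date on which the patient is known to be alive from any source: examination, treatment, visit, telephone, treating physician or vital-status record.
- Set one common cut-off date. Before database freeze, check the vital status of every patient not known to be dead.
- Censor patients known alive at the cut-off on that date, and do not count later deaths. Censor patients who cannot be traced at their latest known-alive date, and report how many there are.
- Keep the new definition away from PFS and hepatic PFS. SAP 7.4.5.1 and 7.4.6.1 now refer to last news, so a wider definition would otherwise lengthen progression-free time without imaging. Protocol XII.2.1 (PFS) and XII.2.2 (hepatic PFS) end these at the last morphological evaluation, and they should stay there.

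The cost is a short SAP change and one status check of at most 58 patients. It deals with both discarded survival time and missed deaths, so the direction of the bias need not be settled first. SAP 4.5 requires changes before the database is frozen.
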